2.3.1 Does this research study involve a placebo-controlled arm?

\* Yes

[reviewer notes¬]

2.3.1.1 Is there a commonly used diagnostic/treatment approach that is currently recognized as being effective for the proposed subjects' disease or condition, and that will be withheld from subjects assigned to the placebo arm of this research study?

No; subjects assigned to the placebo and experimental arms of the research study will continue to undergo a commonly used diagnostic/treatment approach

[reviewer notes¬]

- 2.4 Will any research subjects be withdrawn from known effective therapy for the purpose of participating in this research study?
  - \* No

[reviewer notes¬]

- 2.5 Will screening procedures (i.e., procedures to determine research subject eligibility) be performed specifically for the purpose of this research study?
  - \* Yes
- 2.5.1 List the screening procedures that will be performed for the purpose of this research study. Do NOT include the inclusion/exclusion criteria in this section as they will be addressed in section 3; questions 3.13 and 3.14.

There are two mechanisms in which patients will be effectively screened:

- 1) The study coordinator uses the data listed in the "UPMC Multiple Sclerosis and Related Disorders Registry" (PRO12010609) to identify prospective subjects. Patients have already consented to join this registry and this consent includes provision for information to be accessed by study personnel, with patients explicitly "opting in" to be contacted if they qualify for ongoing studies.
- 2) The care team at the UPMC MS Center (MDs, PAs, nurses, etc.) identify subjects interested in joining the study during the course of ongoing, routine clinical care encounters. Care team members would then provide the contact information of interested subjected to the study coordinator to arrange for the consent process and study initiation.

[reviewer notes¬]

2.6 Provide a detailed description of all research activities (e.g., all drugs or devices; psychosocial interventions or measures) that will be performed for the purpose of this research study.

This description of activities should be complete and of sufficient detail to permit an assessment of associated risks.

At a minimum the description should include:

- all research activities
- personnel (by role) performing the procedures
- location of procedures
- duration of procedures
- timeline of study procedures

RESEARCH PLAN: The goal of this proposal is to determine the efficacy of timed rectal evacuation as a treatment for anorectal dysfunction symptoms in patients with mild-to-moderate severe MS. The primary end-point of the randomized clinical trial is a greater than 30% improvement in patients' subjective global assessment of bowel symptom severity after 4 weeks. In secondary analyses, we will determine the factors predicting treatment response, as well as assess the impact of therapy on measures of global and anorectal dysfunction-related quality of life.

Study Design: This is a single-center, randomized, double-blind placebo controlled trial incorporated into routine clinical care for MS patients with anorectal dysfunction. Patients will be randomized to receive placebo or bisacodyl 10 mg rectal suppositories every other day for 4 weeks.

Study Population and enrollment: Patients at the University of Pittsburgh Medical Center (UPMC) MS Center with anorectal dysfunction will be recruited via either an existing registry, chart review, and/or ongoing care encounters. The UPMC MS Center currently cares for well over 2,000 patients. The study is adequately powered if enrollment reaches 56 patients (see Power Analysis below). To ensure adequate numbers in an intention-to-treat analysis, we will plan for a ~20% patient drop-out rate (thus, enrolling 70 patients in total). Normal clinical care pathways at UPMC naturally generate ~2-3 patient consultations per week for MS patients with anorectal dysfunction (total ~125 patients per year), and the pool of potential study candidates far exceeds that number. Therefore, enrollment of 70 patients appears quite feasible.

Study flow: A schematic of the study flow is shown in the attached figure. All patient encounters, referrals, and tests are integrated into the flow of routine clinical care at UPMC. Recruited patients will meet with the study coordinator in an in-person meeting to discuss the details of the study and obtain informed consent (Kaufman Building MS Clinic). At that time (Phase 1), additional measures of baseline bowel symptom severity and bowel-related quality of life (QOL) will be obtained by standardized questionnaires (see below). The study coordinator will provide patients with instructions on maintaining a daily bowel diary (see Study Measures below), and then initiate referrals for anorectal function testing in the DDC and a later follow-up appointment with the PI/Co-PI ("NeuroGI"). The consent process, baseline questionnaires, and instructions on bowel diary are unlikely to take more than 1 hour of time.

During the next 2-4 weeks after study entry, patients will complete the baseline daily bowel diary.

During Phase 2, patients will meet the PI / Co-PI in the UPMC Digestive Disorders Center (DDC) for anorectal function testing (anorectal sensory and High Resolution Anorectal Manometry (HRAM) testing), which typically takes about 45 minutes. This is a one time, routine test that is performed in patients with anorectal dysfunction. It involves the transanal placement of a thin manometry catheter with inflatable balloon into the rectum. The patients' threshold to first sensation of rectal filling, urgency, and pain, basal anal resting pressure, voluntary anal squeeze pressure, and the rectal-anal inhibitory reflex (RAIR) to rectal distention and during simulated strain, as well as the ability to evacuate a 50 cc volume rectal balloon within one minute are all recorded variables and constitute normal components of such testing. The PI/Co-PI will meet with patients in the DDC GI lab around the time of the anorectal testing, and based on the clinical assessment of dominant bowel symptoms, provide patients with guidance on baseline interventions (either laxative or anti-diarrheal use). For example, the use of oral therapies is predicated on patients' typical stool form (using the Bristol Stool Scale 1-7) - the goal is to achieve a typical bowel movement of a 3-5 in consistency. Patients with Bristol 1-2 stools (hard) will use 8.5 - 42 grams of PEG-3350 laxative per day, while those with Bristol 6-7 (loose) will use 0.5 - 4 grams of loperamide per day, titrated to the goal. At the end of Phase 2 visit, patients will be given instructions on study medication use and will obtain the study drug (double-blinded; study drug "blister" packets would have been previously randomized by the pharmacy and delivered to the DDC). Patients will be encouraged to continue daily bowel diaries for the ensuing 4 weeks of the study trial period. Phase 2, including the physiological testing assessment and meeting with the PI/Co-PI, should take about 1.5 hours in total.

During the next 4 weeks, patients will use recommended oral therapies in addition to the every other day use of the rectal suppository study medication. They will record events in their daily bowel diary.

Finally in Phase 3, after the 4 week study period, patients will meet with the study coordinator to collect unused study medication and completed bowel diaries, and then undergo final reassessments of bowel dysfunction severity and QOL measures. This process could take up to 1 hour. After the questionnaires are completed, patients and the PI/Co-PI will be debriefed (i.e. study arm allocation will be revealed) before having a routine followup clinic visit (continuity of care).

- 1) The study coordinator will identify and screen potential study subjects (by accessing the "UPMC Multiple Sclerosis and Related Disorders Registry" (PRO12010609) to identify prospective subjects), coordinate the informed consent process with the PI/Co-PI, collect intake questionnaires, and provide instruction on bowel diaries (Phase 1). The coordinator will schedule referrals for anorectal function testing and follow-up DDC visit, and contact patients during the 4-week trial period to verify compliance. Finally, the coordinator will collect bowel diaries and remaining medications at study end, administer study exit questionnaires, and then debrief subjects and the PI/Co-PI once the blind is broken (Phase 3).
- 2) DDC GI nursing staff routinely performs HRAM studies and will do so in this study. The PI/Co-PI will be involved in clinical care and recommendations both during Phase 2 and Phase 3 (and beyond).
- 3) MS Physicians will be involved in initial identification of potential subjects and all MS-related continuity of care.
- 4) Falk Pharmacy serves UPMC for clinical trials, and staff will ensure the 1:1 randomization and distribution of either twenty placebo or biscodyl 10 mg rectal suppositories (used every other day over 4 weeks during the study period). Falk Pharmacy staff is experienced in running clinical trials and maintaining double-blind study conditions between subjects and investigators. Patients will receive a slight excess number of suppositories in order to assess study medication compliance at trial end.

STUDY MEASURES: We plan to obtain the following information from all enrolled patients:
1) Primary Patient-Reported Outcome Measure: "Using a scale of 1 to 10 (1 being no problem and 10 being maximally impactful symptoms), how would you rate the severity of your bowel symptoms over the past 2 weeks?"

- 2) Daily Bowel Diaries patients will record the consistency (Bristol Stool Scale, 1-7), number of bowel movements (BM), and occurrence of any fecal incontinence (FI) episodes each day. This data will be used to abstract BM and FI weekly frequency, as well as the mean change in stool consistency during the study period.
- 3) Patient Assessment of Constipation Symptom Questionnaire (PAC-SYM)
- 4) Fecal Incontinence Severity Index (FISI)
- 5) Patient Assessment of Constipation QOL (PAC-QOL)
- 6) Rockwood Fecal Incontinence Quality of Life Scale (FIQL)
- 7) SF-36 health status questionnaire
- 8) Study Medication Compliance
- 9) Anorectal Sensory and High Resolution Anorectal Manometry Testing: First sensation of rectal filling, urgency, and pain, basal anal resting pressure, voluntary anal squeeze pressure, and the rectal-anal inhibitory reflex (RAIR) to rectal distention and simulated strain, as well as the ability to evacuate a 50 cc volume rectal balloon within one minute.

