# AIM 1: Determine the impact of timed rectal evacuation on anorectal dysfunction in MS patients

We will conduct a four week, single-center, randomized, double-blind placebo controlled clinical trial designed to assess the efficacy of timed rectal evacuation in improving the subjective global assessment of bowel symptoms in a cohort of patients with mild-to-moderate severity MS disease. Patients will be randomized 1:1 to administer either placebo or bisacodyl 10 mg rectal suppositories every other day during the 4 week trial. The primary endpoint will be the change in patients' rating of bowel symptom severity (10 point rating scale) at end of 4 weeks compared to baseline values. We will define an adequate treatment response as greater than a 30% reduction in symptom severity using an intention-to-treat analysis.

AIM 2: Determine the predictors of treatment response and impacts on quality of life

We plan to collect information on the patients' assessed severity of baseline and treatment-associated anorectal dysfunction, their impact on quality of life, as well as daily bowel diaries. Patients also will undergo anorectal sensory and manometric testing as a part of their routine clinical care. Enrolled patients that complete the study will be assessed for study medication compliance. All of these measures will be used to explore factors that are associated with treatment response. Changes in assessments of anorectal dysfunction-related quality of life will serve as key secondary end-points.

This proposal will significantly advance MS care and management by developing the evidence to support the adoption of a simple, safe, and cost-effective clinical treatment algorithm for anorectal dysfunction in the MS population. This paradigm for anorectal dysfunction management could be applicable to a majority of MS patients, and the treatment algorithm could be introduced to patients by nurses or mid-level clinical providers during points of routine MS patient care. Importantly, the treatment could be effectively accomplished by most patients and their caregivers at home. The findings of this investigation could also have a broader influence on care models for anorectal dysfunction associated with a range of other neurological illnesses, such as Parkinson's Disease, ALS, or stroke.

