#### SECONDARY END POINTS:

1) Daily Bowel Diaries – patients will record the consistency (Bristol Stool Scale, 1-7), number of bowel movements (BM), and occurrence of any fecal incontinence (FI) episodes each day. This data will be used to abstract BM and FI weekly frequency, as well as the mean change in stool consistency during the study period.

- 2) Patient Assessment of Constipation Symptom Questionnaire (PAC-SYM)
- 3) Fecal Incontinence Severity Index (FISI)
- 4) Patient Assessment of Constipation QOL (PAC-QOL)
- 5) Rockwood Fecal Incontinence Quality of Life Scale (FIQL)
- 6) SF-36 health status questionnaire
- 7) Study Medication Compliance
- 8) Anorectal Sensory and High Resolution Anorectal Manometry Testing: First sensation of rectal filling, urgency, and pain, basal anal resting pressure, voluntary anal squeeze pressure, and the rectal-anal inhibitory reflex (RAIR) to rectal distention and simulated strain, as well as the ability to evacuate a 50 cc volume rectal balloon within one minute.
- 2.18 Describe the statistical approaches that will be used to analyze the study data.
  - \* Addressed below:

Categorical data will be analyzed using Fisher's Exact tests for differences in proportions. Continuous data will be analyzed using Student's t-tests to detect differences in group means, with Bonferroni correction for multiple comparisons. We will use logistic regression to determine the factors that predict treatment responses.

A p<0.05 will be used as the threshold for statistical significance in all cases.

POWER ANALYSIS/SAMPLE SIZE: It is generally regarded that a 3-point reduction represents a clinically meaningful change using such a 10 point scale, and similar research studies using patient-reported outcomes have reported standard deviations ranging around ~2.5 points. However, we do not have baseline data to estimate variance, and thus we took a conservative estimate with an expected standard deviation of 4 points. Given these assumptions, we will need 28 patients in each study arm to detect at least a 30% reduction in symptom severity, with a power of 0.80, alpha=P<0.05 in a two-tailed analysis.

[reviewer notes-]

- 2.19 Will this research be conducted in (a) a foreign country and/or (b) at a site (e.g., Navajo Nation) where the cultural background of the subject population differs substantially from that of Pittsburgh and its surrounding communities?
  - \* No

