3.8 Does this research study involve neonates of uncertain viability or nonviable neonates?

\* No

[reviewer notes¬]

- 3.9 Fetal Tissues: Does this research involve the use of fetal tissues or organs?
  - \* No

[reviewer notes¬]
--->

3.10 What is the total number of subjects to be studied at this site, including subjects to be screened for eligibility?

Note: The number below is calculated by summing the data entered in question 3.11. Any additions or changes to the values entered in 3.11 will be reflected in 3.10.

- \* 400
- 3.11 Identify each of the disease or condition specific subgroups (include healthy volunteers, if applicable) that will be studied.

Click on the "Add" button and specify for each subgroup:

- 1) how many subjects will undergo research related procedures at this site; and
- 2) if applicable, how many subjects will be required to undergo screening procedures (e.g., blood work, EKG, x-rays, etc.) to establish eligibility. Do Not include subjects who will undergo preliminary telephone screening.

\*

Subgroup	Number to undergo research procedures	Number to undergo screening procedures
View MS patients	70	400

- 3.12 Provide a statistical justification for the total number of subjects to be enrolled into this research study at the multicenter sites or this site.
  - \* Described below:

The primary outcome measure is the group mean difference in subjective severity ratings of bowel symptoms using a 10 point scale. It is generally regarded that a 3-point reduction represents a clinically meaningful change using such a scale, and similar

Section: Section 3 - Human Subjects

research studies using patient-reported outcomes have reported standard deviations ranging around ~2.5 points on a 10 point scale. However, we do not have baseline data in this population to estimate variance, and thus we took a conservative estimate with an expected standard deviation of 4 points. Given these assumptions, we will need 28 patients in each study arm to detect at least a 3 point reduction in symptom severity, with a power of 0.80, alpha=P<0.05 in a two-tailed analysis.

Thus, the study is adequately powered if enrollment reaches 56 patients. However, to ensure adequate numbers in an intention-to-treat analysis, we will plan for a ~20% patient drop-out rate. Therefore, we will aim to enroll 70 patients in total.

[reviewer notes¬]

3.13 Inclusion Criteria: List the specific criteria for inclusion of potential subjects.

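### Optional precision gain, not an error: repeat the 1-10 severity item at the Phase 2 visit and use the mean of the two pre-treatment ratings as baseline

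*Combined protocol and SAP*

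**What the plan says.** Aim 1 (section 1.2) makes the primary endpoint the "change in patients' rating of bowel symptom severity (10 point rating scale) at end of 4 weeks compared to baseline values". Section 3.12 states: "The primary outcome measure is the group mean difference in subjective severity ratings of bowel symptoms using a 10 point scale". Sections 2.6 and 2.17 instead give a responder endpoint, "greater than 30% improvement in patients' subjective global assessment of bowel symptom severity after 4 weeks". For the analysis, section 2.18 says: "Continuous data will be analyzed using Student's t-tests to detect differences in group means". It names Fisher's exact test for proportions and no baseline adjustment.

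On timing, section 2.6 says of the Phase 1 visit that "additional measures of baseline bowel symptom severity and bowel-related quality of life (QOL) will be obtained by standardized questionnaires". Section 5.16 also treats Phase 1 as the point where baseline measures are taken. Then: "During the next 2-4 weeks after study entry, patients will complete the baseline daily bowel diary". The Phase 2 description lists anorectal testing, guidance on oral laxatives or loperamide, and dispensing of study drug at the end of the visit. It lists no severity rating. The final rating is at Phase 3, after 4 weeks. The item asks about the preceding 2 weeks.

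On variability, section 2.18 says that "similar research studies using patient-reported outcomes have reported standard deviations ranging around ~2.5 points", but that "we took a conservative estimate with an expected standard deviation of 4 points".

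**The concern.** The change score and the >30% rule both depend on one answer to one item, given 2-4 weeks before treatment starts and so 6-8 weeks before the final rating. Because the item looks back 2 weeks, that answer describes the fortnight before consent and none of the run-in. A rating on arrival at Phase 2 would be about 4 weeks before the final one. Its recall window would adjoin the Phase 1 window if the gap is 2 weeks, and lie 2 weeks after it if the gap is 4.

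What is at stake is precision only. The sponsor says it has no variance data for this population, and the trial has 70 patients at one centre. A visit already exists at which a second pre-treatment rating could be taken.

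**Working it through.** **The plan's own figure.** Inputs from sections 2.18 and 3.12: difference 3, SD 4, two-sided alpha 0.05, power 0.80. By the normal approximation, n per arm = 2 × (1.96 + 0.84)² × 4² / 3² = 27.9, so 28 (power 0.801). The t-based solution is 28.9, with power 0.787 at 28 per arm. Then 56 / 0.8 = 70. The stated figures reproduce.

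**Variance of the change score.** Assume equal rating variance at each visit, set to 1. Let r12, r13 and r23 be the correlations of Phase 1 with 2, Phase 1 with 3, and Phase 2 with 3. The plan gives none, so all are assumptions.

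- Phase 1 alone: 2 − 2·r13
- Mean of Phases 1 and 2: 1 + (1 + r12)/2 − r13 − r23

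The mean is better whenever r13 − r23 < (1 − r12)/2. That always holds if Phase 2 predicts the outcome at least as well as Phase 1 and r12 < 1.

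With r13 = r23 = r:

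| r | r12 | Phase 1 alone | Mean of two | Reduction |
|---|---|---|---|---|
| 0.3 | 0.3 | 1.40 | 1.05 | 25% |
| 0.3 | 0.5 | 1.40 | 1.15 | 17.9% |
| 0.5 | 0.5 | 1.00 | 0.75 | 25% |
| 0.5 | 0.7 | 1.00 | 0.85 | 15% |

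**Why r stops at 0.5 for the SD 4 case.** If the SD of change is 4, the rating SD is 4/√(2 − 2r): 3.4 at r = 0.3, 4.0 at r = 0.5 and 5.2 at r = 0.7. The largest SD possible on a 1-10 scale is about 4.5 (half the patients at each end). So r cannot exceed 1 − 16/(2 × 4.5²) = 0.60.

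**t-test power for 3 points, 28 per arm.**

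| SD of change | One baseline | 15% reduction | 25% reduction |
|---|---|---|---|
| 4 | 0.787 | 0.85 | 0.889 |
| 2.5 | 0.993 | 0.998 | 0.999 |

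At SD 4 the difference detectable with 80% power falls from 3.05 to 3.05 × √0.85 = 2.81, or 3.05 × √0.75 = 2.64.

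**Correlation that decays with time.** With 0.7 between adjacent visits and 0.49 between Phases 1 and 3, the variances are 1.02 (Phase 1), 0.66 (mean) and 0.60 (Phase 2 alone). The mean is then not the best choice, but it still clearly beats Phase 1.

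**Covariate adjustment.** With equal correlations, the residual variance is 1 − r² with one baseline and 1 − 2r²/(1 + r) with the mean of two.

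| r | Adjusted, one baseline | Adjusted, mean of two | Reduction | Change score, mean of two |
|---|---|---|---|---|
| 0.3 | 0.91 | 0.86 | 5% | 1.05 |
| 0.5 | 0.75 | 0.67 | 11% | 0.75 |
| 0.7 | 0.51 | 0.42 | 17% | 0.45 |

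With the same mean baseline, adjustment is more precise than the change score in every row.

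**Responder rule (simulation, assumed inputs).** With rating SD 2.5, baseline mean 7, mean drops of 1 and 3 points and 28 per arm, Fisher power goes from 0.52 to 0.59 (r = 0.3), 0.64 to 0.71 (r = 0.5) and 0.80 to 0.86 (r = 0.7). Over wider sets of inputs the gain is roughly 2.5-13 points. It can drop to about 0.8 where the assumptions are least favourable.

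**The case against.** A single baseline is standard practice, so nothing in the plan needs correcting. That stands.

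The t-test gain is largest in a case that is hard to reach. An SD of change near 4 needs ratings spread almost as widely as the scale allows, and the sponsor calls 4 conservative. At the cited 2.5, power for 3 points is already near 1. This stands for the t-test. It does not dispose of the responder comparison, where the simulated gains come from a rating SD of 2.5.

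Adjusting the final rating for the existing Phase 1 score needs no new data. At r of 0.5 or less it equals or beats the two-baseline change score (0.91 v 1.05 at r = 0.3; 0.75 v 0.75 at r = 0.5). This also stands, and it is why the averaged baseline is better used as a covariate. The second rating then still adds something, but less.

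The gain also depends on which primary analysis applies. If section 3.12 means final ratings compared without adjustment, a second baseline changes nothing in that test.

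The Phase 1 sentence does not name the 1-10 item, and neither the study diagram nor the uploaded questionnaire was available. A Phase 2 rating may already exist.

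A reader might infer that a baseline 2-4 weeks old biases the result, or that the trial is underpowered as designed. The documents support neither. Both arms are rated on the same schedule, both receive the oral-agent guidance, and the sample size reproduces. Nor would a second rating separate the effect of the oral agents from that of the suppository.

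**Conclusion.** The point holds as an optional, low-cost improvement and as nothing stronger. As described, the severity item is rated once before treatment, although the Phase 2 visit offers a natural second occasion. Under assumed correlations of 0.3-0.5, averaging two ratings cuts change-score variance by about 15-25%. That is useful if the SD of change is near 4 and negligible for a 3-point difference if it is near 2.5. The responder comparison gains roughly 2.5-13 points of power in illustrative settings, and a covariate-adjusted analysis gains about 5-17% in variance (r = 0.3-0.7, equal correlations). Every one of these sizes rests on correlations that the plan does not supply. No bias is corrected.

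**What to change.** First check the study diagram and questionnaire for an existing Phase 2 rating. If there is none:

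- In section 2.6, have patients answer the same single item on arrival at Phase 2, before anorectal testing, oral-therapy guidance and dispensing. Use paper or a named existing team member, because the coordinator is not described as present at that visit.
- In section 2.18, define baseline as the mean of the Phase 1 and Phase 2 ratings, or Phase 1 alone if Phase 2 is missing, for both the change score and the >30% rule. Preferably also use it as a covariate in an analysis of the final rating.
- Fix this definition before any unblinded data are seen. Allocation is revealed patient by patient after Phase 3, so that means before the first patient finishes.

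The cost is one more item at a visit of about 1.5 hours, one more value to record, and short edits to two sections. The sample size and visit schedule stay as they are.

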#### Describe the benefit:

Most patients are likely to see some subjective improvement in bowel function (even those in the placebo arm), since all patients will be will be recommended to use some intervention to alter stool form (i.e. laxatives or anti-diarrheals). The study participants assigned to the active medication arm may derive subjectively greater improvement in bowel related symptoms (the primary hypothesis).

5.13 Describe the data and safety monitoring plan associated with this study. If the research study involves multiple sites, the plan must address both a local and central review process.

The Principal Investigator, [name], will meet with [name] (Co-PI) every 8 weeks to evaluate the progress of the research study, including assessment of data quality and subject recruitment.

Data and Safety will be further monitored by a joint meeting every 6 months between the PI, Co-PI, and [name], a nurse manager of the UPMC MS Clinic who oversees clinical trials for the group. This group will be responsible for the following: 1) reviewing the data accumulated from the ongoing study; 2) advising the principal investigator or study sponsor of necessary changes to elements of the study that affect subject safety; 3) determining whether there has been any change to the risk-to-benefit assessment during the course of the study; and 4) determining whether the study should continue as designed. They will also review, on an ad hoc basis, any serious adverse events (SAE) that are directly related to the study medication as given according the study protocol. The results of the DSMB meetings will be submitted to the IRB at the time of the annual renewal.

[reviewer notes¬]

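### Section 2.6 gives the loperamide dose as 0.5 to 4 grams a day; the unit is very likely wrong and must be checked and corrected before the text is used

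*Combined protocol and SAP*

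**What the plan says.** Section 2.6 describes the visit at which the PI or Co-PI advises each patient on oral treatment to bring stool form to Bristol 3 to 5. One sentence gives the doses for both agents. For hard stools: "Patients with Bristol 1-2 stools (hard) will use 8.5 - 42 grams of PEG-3350 laxative per day". For loose stools: "those with Bristol 6-7 (loose) will use 0.5 - 4 grams of loperamide per day, titrated to the goal".

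The same section carries the oral treatment into the randomized period: "During the next 4 weeks, patients will use recommended oral therapies in addition to the every other day use of the rectal suppository study medication". Section 5.12 adds that all patients, including those on placebo, will be "recommended to use some intervention to alter stool form (i.e. laxatives or anti-diarrheals"). The abstract (CS2.1) is narrower and has these agents given only where indicated.

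Loperamide is named nowhere else in the documents available for review. They give no unit strength, no dose in milligrams and no separate maximum for it. The consent pages and the study diagram are not among them.

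**The concern.** Grams suit the first agent in the sentence, a laxative dosed at 8.5 to 42 g. The second agent carries the same unit, and the resulting daily amount looks far too large for a drug taken in small dose units. The study drug itself, bisacodyl, is given in milligrams throughout. The likeliest explanation is that the unit was carried over from PEG-3350.

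What is at stake is patient safety. Section 2.6 is where the IRB reads what will be done to patients and judges the risk. A wrong unit there means that the dose reviewed is wrong, and anyone preparing patient instructions from the text could repeat it. Both arms are exposed, because the oral agent is background treatment and is not randomized.

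**Working it through.** The protocol does not derive the dose, so there is no calculation to reproduce. The check is a unit conversion.

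**Inputs**
- Loperamide, printed range: 0.5 to 4 g per day (Section 2.6, Phase 2).
- PEG-3350, printed range: 8.5 to 42 g per day (same sentence), used only to compare the unit.
- Loperamide content of one dose unit: not in the documents. Assumed to be 1 to 4 mg, with the whole range shown.

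**Conversion**
- 0.5 g × 1000 = 500 mg per day.
- 4 g × 1000 = 4000 mg per day.

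**Dose units per day = daily dose in mg ÷ mg per unit**

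| Assumed mg per unit | As printed, low end | As printed, high end | If mg were meant |
|---|---|---|---|
| 1 | 500 ÷ 1 = 500 | 4000 ÷ 1 = 4000 | 0.5 to 4 |
| 2 | 500 ÷ 2 = 250 | 4000 ÷ 2 = 2000 | 0.25 to 2 |
| 4 | 500 ÷ 4 = 125 | 4000 ÷ 4 = 1000 | 0.125 to 1 |

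The smallest figure for the printed text is 125 units a day, and the largest is 4000.

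**Sensitivity to the assumption.** For the top of the range to come down to 10 units a day, each unit would have to hold 4000 ÷ 10 = 400 mg, which is 100 times the highest strength assumed. For the bottom of the range the figure is 500 ÷ 10 = 50 mg, or 12.5 times the highest strength assumed. The conclusion does not turn on the exact strength.

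**What the last column shows.** Replacing grams with milligrams removes the implausibly large counts, but the low end becomes half a unit or less at every assumed strength. The numbers themselves may therefore need correction as well as the unit, and the documents cannot settle this.

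**Other places that might catch the error**
- The risk table in Section 5.1 lists side effects of bisacodyl and none of loperamide.
- Section 5.7 foresees no circumstance for discontinuing a subject.
- The ad hoc review of serious events in Section 5.13 covers those directly related to the study medication, which need not include loperamide.
- The pharmacy's role in Section 2.6 covers only the suppositories.

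**The case against.** The strongest reply has three parts.

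First, nothing in the documents proves the error. The sentence is internally consistent, with two agents and two ranges in grams, and the implausibility rests on a unit strength that the documents do not state. That is true, and for that reason the strength is labelled an assumption. The sensitivity figures show that it would have to be wrong by a very wide margin to rescue the printed dose. The explanation that the unit came from PEG-3350 is an inference and cannot be demonstrated.

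Second, the route from this text to a patient is limited. The doses are introduced as an example. The PI or Co-PI, who belong to a gastroenterology motility group, give the advice in person after a clinical assessment, and the dose is titrated to stool form. No section describes loperamide being dispensed from this line. The coordinator contacts patients during the 4 weeks and patients may call staff at any time (Sections 2.6 and 5.1.1). A dose this far out is also less likely to be followed than a plausible wrong one. All of this lowers the chance of harm. It does not make the text right: the sentence tells patients what they will take, and it is the only dosing rule given for this agent. The contacts with patients would come after dosing has begun.

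Third, exposure is narrow. The figure appears once and concerns only patients with Bristol 6 to 7 stools, whose number the documents do not give. That stands. An error in reading the PDF cannot be fully excluded either, but the unit is a whole word in an intact sentence, and the check proposed would settle the matter.

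**Conclusion.** The concern holds, and the correction must be made before the text is used. As printed, Section 2.6 has patients with loose stools take 500 to 4000 mg of loperamide a day, which is 125 to 4000 dose units if a unit holds 1 to 4 mg. Confidence is high that the printed figure is wrong. It is lower on how the error arose and on what was meant: milligrams is the likely unit, but the documents do not confirm it.

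This is a dosing-text and safety point. The oral dose enters neither the endpoint definition nor the sample-size calculation nor the planned tests, so none of these changes.

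**What to change.** Before any use, the PI or Co-PI, together with a pharmacist, should check the loperamide unit and both ends of the range against the product label. They should then correct Section 2.6 and any patient instructions that repeat the figure, and notify the IRB. No replacement dose is proposed here, because the documents do not supply one.

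The cost is one label check, a correction of the unit (and of the range if needed) and an IRB notification. The design, the sample size and the analysis stay as they are.
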